Patients receiving SOC undergo the risk of increased corneal keratopathy. In addition, patients receiving the SOC have an increased risk of post injection pain. The risk of mild ocular discomfort

with CA is mitigated by the use of proparacaine and also poses less risk to patients than topical lidocaine.

1.3.1 Primary Objective:

We plan to carry out a pilot study to collect preliminary data on the effectiveness of the cryoanesthesia (CA) device in minimizing the pain caused by intravitreal injections (IVT) and determine the most effective temperature and time of treatment. Specifically, we intend to record patients' subjective injection pain. The study will be carried out in patients receiving bilateral injections, and one eye will be anesthetized using the CA device, with the fellow eye receiving anesthesia via a topical lidocaine gel (SOC), a common method of providing anesthesia in current clinical practice.

1.3.2 Exploratory Objective(s):

We will measure injection preparation pain, 4-hr, and 24-hr post injection pain. Patients will rate ocular irritation immediately after injection as well as 4 and 24 hours after injection (1 – no irritation; 2 – mild irritation 3 – moderate irritation 4- marked irritation). Patients will rate visual function in the treated eye immediately after injection as well as 4 and 24 hours after injection (1 – no changes from baseline; 2 – mild blurring of vision 3 – moderate blurring of vision 4- marked blurring of vision). Physicians will record patients' objective response to intraocular needle penetration (1 – no pain/movement; 2 – mild pain/movement 3 – marked pain/movement with the injection). In addition, physicians will record the following common ocular side effects following IVT: subconjunctival hemorrhage (SCH), conjunctival hyperemia, and conjunctival injection. These will be assessed via a slit lamp examination performed within 30 minutes and 24 hours of the administration of the intravitreal injection. In addition, each eye will be assessed for other signs of anterior segment toxicity, including AC reaction or hypotony. Patients will be examined or receive a call 1 week after the injection to assess any adverse effects.

1.4 Anticipated duration of the clinical investigation:

[figure not shown]

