treatment will be marked. Next, one drop of proparacaine will be applied into the eye to receive at least 5 minutes before any additional steps. Once the patient is ready, another drop of proparacaine will be applied and the physician or his assistant will then swab the lids with betadine. The patient will then have lidocaine gel placed on the eye and left in place for a minimum of 3 minutes prior to IVT. The 3-minute waiting period is needed to allow the lidocaine gel to diffuse through the sclera. Following completion of numbing, the eyelids will be swabbed with betadine and the physician will place the lid speculum. The physician will use a caliper to measure 3 or 4 mm from the limbus of the eye, place a drop of betadine over this spot, wait 20 seconds and then administer the injection.

2.3.2.1 Allocation to Treatment:

Patients will be randomly assigned to 1 of the 4 CA treatment groups and the SOC arm. Patients will be randomized to have their first eye receive either CA or SOC.

2.3.2.2 Treatment Adherence/Study Compliance:

If a patient is does not require, or refuses, an injection in either eye, they will be removed from the study. Because IVT prevents blindness, the refusal of IVT is extremely rare. In addition, it is extremely rare for patient who have been determined to need IVT to have improvement in vision prior to IVT.

If patients withdraw from the study, we will plan to recruit additional patients to replace them.

2.3.3 **Follow-up Procedures:**

2.3.3.1 Procedures to Assess Efficacy:

Patients will record their subjective pain (pre-injection preparation pain, injection pain, and 24 hr post injection pain) using a visual analog scale (1 to 10, with 10 being severe pain and 1 being no pain). The study coordinator will call the patients within 4 hours after their injection to review their 4-hr post procedure pain scores with them. Patients will be asked to return in 24 hours for anterior segment examination and 24-hr post injection pain assessment. Patients treated on Friday will be asked to return on Saturday for their 24-hr post injection assessment.

2.3.3.2 Procedures to Assess Safety:

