In accordance with applicable policies of the University of Michigan Institutional Review Board (IRBMED), the investigator-sponsor will report, to the IRB, any observed or volunteered adverse effect that is determined to meet all of the following criteria: 1) *associated with the investigational device or, if applicable, other study treatment or diagnostic product(s)*; 2) *a serious adverse effect*; and 3) *an unexpected adverse effect*. Adverse event reports will be submitted to the IRB in accordance with the respective IRB procedures.

Applicable adverse effects will be reported to the IRB as soon as possible and, in no event, later than 10 calendar days following the investigator-sponsor's receipt of the respective information. Adverse effects which are 1) *associated with the investigational drug or, if applicable, other study treatment or diagnostic product(s)*; 2) *fatal or life-threatening*; and 3) *unexpected* will be reported to the IRB within 24 hours of the investigator-sponsor's receipt of the respective information.

Follow-up information to reported adverse effects will be submitted to the IRB as soon as the relevant information is available. If the results of the sponsor-investigator's follow-up investigation show that an adverse effect that was initially determined to not require reporting to the IRB does, in fact, meet the requirements for reporting; the investigator-sponsor will report the adverse effect to the IRB as soon as possible, but in no event later than 10 calendar days, after the determination was made.

3.1 Withdrawal of Subjects Due to Adverse Effects:

Patients will only have a single exposure to the device (10 to 20 seconds in length). Should a patient not tolerate the discomfort of the cold tip for the entire duration and be unable to receive full CA, that patient would be removed from the study.

If a patient withdraws from the study, the patient data will be destroyed. Another patient will be recruited to take their place, provided that the additional patient can be recruited and treated within the allotted study time frame.

3.2 Monitoring Plan:

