- Check and review of the regulatory binder and all essential documents
- Review of all SAEs and subject withdrawals
- Enrollment issues and targets
- Protocol amendments and their approval by the IRB
- Protocol deviations
- Personnel changes and required training
- Verifying continuous institutional review board (IRB) approval
- Any other issue as deemed important to the conduct of the study

Reporting and Follow-up:

If there are any significant findings, the S-I will follow-up any noncompliance, potential noncompliance, data irregularities, or other deficiencies identified along with a description of any actions taken, to be taken, or recommended, including the person responsible for completing actions and the anticipated date of completion.

4.0 Description of the Investigational Device:

Prototype Description:

The cryo-anesthesia device is a handheld instrument measuring approximately 10 inches in length and 1.5 inches in diameter, and weighing 0.8 pounds. A $4 \times 4 \text{ mm}^2$ area at the tip of the device is placed against the eye and cooled to a user-specified temperature setpoint between -5 and -10°C via activation of a switch on the device (**Figure 2**). The temperature setpoint is selected prior to device activation. Ocular surface cooling slows conduction of pain fibers in the conjunctiva (outermost layer of the eye) and the sclera (white of the eye) to a depth less than a millimeter. The key features of the device include a temperature regulating feedback loop that maintains highly accurate and precise temperature control and an integrated timer that controls the duration of cooling, both of which facilitate sufficient cooling and prohibit excessive cooling. Two small protrusions on the tip leave temporary indentations on the surface of the eye to guide placement of the intravitreal needle. The cooling region of the device is located on a replaceable metal tip. An “ON” switch is first activated to cool the contact region of the device, after which this region is placed against the eye, initiating rapid cooling to anesthetize the injection site while simultaneously marking the cooled location. After the specified cooling time is reached, the device is removed, immediately after which the physician performs intravitreal injection.

Figure 2 | Cryoanesthesia device.

Safety Features:

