A user readies the device by first inserting the replaceable tip into the cold arm. A vice-like mechanism (7 in Fig. 3) is used to provide both convenient tip replacement and sufficient pressure between the replaceable tip and cold arm for good thermal contact. The replaceable tip is coated by a thin hydrophobic polymer layer that mitigates ice adhesion between the device and tissue. Two small protrusions (8 in Fig. 3) on the replaceable tip leave temporary indentations on the eye surface to guide subsequent treatment (e.g., placement of the intravitreal injection needle 3 or 4mm from the corneal limbus).

After setting the desired cold tip temperature setpoint and timer duration and inserting the replaceable tip, the user operates the device by first double-pressing the main (“rotation & push”) button, which turns on the Peltier modules and brings the tip temperature to the setpoint (this takes approximately 20 seconds for a setpoint of -10°C). He or she then brings the tip into contact with the patient’s eye and presses the “timer” button (which responds with a beep). If the timer duration is set to 10 (or 30) seconds, the device maintains -10 °C for 10 (or 30) seconds and then beeps. After the timer duration, the device returns to ambient temperature.

There are no anticipated changes to the device during the course of this study.

5.0 Future Studies:

We plan to conduct a second phase of the study where we will compare the SOC to only one cryoanesthesia temperature setpoint and one time setpoint, selected after the analysis of the first 40 patients.

References:

Beckman, H., S. Leff and H. S. Sugar (1975). "Scleral bursting strength. Results after treatment with ruby laser, cryotherapy, or diathermy." *Arch Ophthalmol* **93**(6): 428.

Blaha, G. R., E. P. Tilton, F. C. Barouch and J. L. Marx (2011). "Randomized trial of anesthetic methods for intravitreal injections." *Retina* **31**(3): 535-539.

Chi, H. H. and C. D. Kelman (1967). "Histopathology of corneal endothelium after freezing." *Int Ophthalmol Clin* **7**(2): 369-380.

Curtin, V. T., T. Fujino and E. W. Norton (1966). "Comparative histopathology of cryosurgery and photocoagulation. Observations on the advantages of cryosurgery in retinal detachment operations." *Arch Ophthalmol* **75**(5): 674-682.

Davis, M. J., J. S. Pollack and S. Shott (2012). "Comparison of topical anesthetics for intravitreal injections : a randomized clinical trial." *Retina* **32**(4): 701-705.

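### Section 3.1 removes randomised patients who cannot complete cryoanesthesia and does not say their data are kept, so the setpoint choice rests on completers and intolerance by setpoint goes uncounted

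*Protocol*

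**What the plan says.** All references are to the Protocol.

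- **Section 3.1, first paragraph.** A patient who does not tolerate the cold tip for the whole duration and would "be unable to receive full CA, that patient would be removed from the study".
- **Section 3.1, second paragraph.** "If a patient withdraws from the study, the patient data will be destroyed". Then: "Another patient will be recruited to take their place, provided that the additional patient can be recruited and treated" within the study time frame.
- **Section 2.3.2.2.** A patient who "does not require, or refuses, an injection in either eye, they will be removed from the study". It adds: "If patients withdraw from the study, we will plan to recruit additional patients to replace them".
- **Section 2.3.2.1.** Patients are randomised to one of four CA groups and to standard of care (SOC). Section 2.3.2 has the physician check the arm's temperature and time before the tip touches the eye.
- **Section 1.3.1.** The primary objective is partly to "determine the most effective temperature and time of treatment".
- **Section 5.0.** One temperature and one time go into a second phase, "selected after the analysis of the first 40 patients".
- **Section 2.2.2.** 40 patients, 10 per CA group, all expected to complete.
- **Section 3.2.** The two monitoring meetings cover device-use documentation and "Review of all SAEs and subject withdrawals".

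Neither the primary endpoint nor any of the nine exploratory endpoints in section 2.4.1 records failure to complete CA.

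**The concern.** The rule excludes patients because of what happened to them under their randomised setting. Inability to complete CA is one direct way in which a temperature or time can fail, and cold discomfort is the device risk that section 1.3 names. If these patients leave the study and are replaced, every setting appears in the analysis as fully tolerated, whatever happened in the clinic.

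Two things are at stake. First, the number of patients who could not complete CA at each setpoint, a basic result for a pilot that selects a setpoint, is neither defined as an outcome nor linked to the selection. Second, if patients who cannot stand the cold also tend to report more injection pain, the mean among completers flatters the settings that lose most patients. Preparation pain, the endpoint closest to cold discomfort, would be lost for the same patients if their data are destroyed.

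**Working it through.** **Step 1: what happens to a removed patient's data.** Section 3.1 uses *removed* for the intolerant patient and *withdraws* for the patient whose data are destroyed. Both sit under one heading about withdrawal due to adverse effects, and no other passage governs the removed patient's data. Two readings are possible:

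- Removal counts as withdrawal: the data are destroyed and the patient is replaced.
- Removal is something else: the patient is out of the study and the protocol does not say what becomes of the data.

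Under either reading the patient is not among those from whom the setpoint is chosen.

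**Step 2: the protocol's own figure.** 4 groups × 10 = 40 reproduces. The protocol gives no intolerance rate, SD or correlation, so every input below is an assumption. The intolerance rate q is taken as 2%, 5%, 10% and 20%.

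**Step 3: how many patients would disappear.** Expected removals while filling n completers = n·q/(1−q). Chance that at least one of a group's first 10 cannot complete = 1−(1−q)^10.

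| q | Removed, one group (n = 10) | Removed, all four groups at this rate (n = 40) | At least one of the first 10 |
|---|---|---|---|
| 2% | 0.20 | 0.82 | 18% |
| 5% | 0.53 | 2.11 | 40% |
| 10% | 1.11 | 4.44 | 65% |
| 20% | 2.50 | 10.0 | 89% |

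Example: 1 of 11 randomised patients cannot complete (9%, exact 95% CI 0.2% to 41%). After removal and replacement the analysed group shows 0 of 10 (CI 0% to 31%).

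**Step 4: bias in mean injection pain.** Let a latent intolerance score have correlation ρ with injection pain (SD 2), and remove the top fraction q. The completers' mean is then too low by ρ·2·φ(z)/(1−q), where z is the 1−q normal quantile. At q = 10%, z = 1.282 and φ(z) = 0.1755, so with ρ = 0.5 the shift is 0.5 × 2 × 0.1755/0.9 = 0.195.

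Each patient is their own control, so the bias in CA minus SOC replaces ρ by ρ_CA − ρ_SOC. With ρ_CA = 0.5:

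| q | ρ_SOC = 0 | ρ_SOC = 0.25 | ρ_SOC = 0.5 |
|---|---|---|---|
| 2% | 0.049 | 0.025 | 0 |
| 5% | 0.109 | 0.054 | 0 |
| 10% | 0.195 | 0.097 | 0 |
| 20% | 0.350 | 0.175 | 0 |

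The ρ_SOC = 0 column is also the shift in the CA mean alone. If intolerance is unrelated to injection pain, that shift is zero.

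**Step 5: effect on the setpoint choice.** Simulation of 200,000 trials: four equally good settings of 10 patients, intolerance in one setting only, removed patients replaced, settings ranked on mean CA minus SOC, CA and SOC pain otherwise independent. With no bias, the affected setting ranks best in 25% of trials.

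| q | ρ_SOC = 0 | ρ_SOC = 0.25 | ρ_SOC = 0.5 |
|---|---|---|---|
| 2% | 26% | 26% | 25% |
| 5% | 28% | 27% | 25% |
| 10% | 31% | 28% | 25% |
| 20% | 36% | 31% | 25% |

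The model treats the 1 to 10 scale as an unbounded normal variable. It also compares completers with the mean that would arise if everyone had received full CA. It does not model pain after partial CA.

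**The case against.** The strongest reply is that destruction is tied to patients who withdraw, not to those who are removed, so the irreversible harm is an inference. That is right as to the wording. It does not rescue the rule: the alternative reading leaves the data ungoverned, and removal alone takes the patient out of the analysis.

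A second reply is that intolerance would not vanish entirely. Section 3.2 provides for review of withdrawals, device-use documentation and adverse events, and holding each group at 10 by replacement requires knowing the removed patient's group. This stands in part: a bare count may survive. But nothing requires it to be tabulated by setpoint or used in the selection. Reviewing withdrawals as events is also not strictly incompatible with destroying outcome data, so the tension between 3.1 and 3.2 is a minor point on which the conclusion does not depend.

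Third, intolerance may be rare. Exposure is 10 to 20 seconds after proparacaine, the protocol calls the discomfort mild, and it expects all 40 to complete. At 2% to 5% the pain bias is small and may be zero, and a single case in a group of about 10 barely separates settings. All of this stands, and it limits the claim about pain bias. It does not justify taking the cases that would test the expectation out of the analysis.

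Finally, the choice of analysis set usually belongs to the SAP, which is not at hand. But removal, destruction and replacement are conduct rules fixed in the protocol, and no SAP can analyse data that were destroyed or never collected.

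**Conclusion.** The concern holds and should be corrected before any patient is handled under the rule. Followed as written, section 3.1 bases the setpoint choice on CA completers, and no endpoint counts incomplete CA by setpoint. That loss needs no assumption about how intolerance relates to pain.

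The size of the pain bias is unknown. Under the assumed SD of 2 and a CA correlation of 0.5, it runs from zero to about 0.35 points across 2% to 20% intolerance, and is at most 0.11 at 5% or below. The corresponding distortion of the ranking runs from none to 36% against a fair 25%. Destruction of removed patients' data is the natural reading, not an explicit statement. The rule in section 2.3.2.2 on refused or unneeded injections is not specific to CA, but it leaves the same question about data open.

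**What to change.** In section 3.1, separate inability to complete CA from withdrawal of consent. Suggested text:

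> A patient who does not complete CA is recorded as incomplete CA, with the assigned setpoint and the reason. Data on this patient are retained under the randomised CA group and are not destroyed. Any replacement is additional to this patient. Withdrawal of consent is recorded separately, and data are then handled as the consent form states. Incomplete CA due to intolerance is reported by setpoint over all randomised patients and considered when the setpoint for the second phase is selected.

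In addition:

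- State whether pain scores are still collected after incomplete CA when the patient agrees. Where an injection-pain score exists, include it and show the completers-only result beside it. Any worst-rank scoring can be left to the SAP.
- In section 2.3.2.2, count refused or unneeded injections separately with reasons, not as CA failures, and say whether those data are kept.
- Reconcile sections 3.1 and 2.3.2.2 with the withdrawal review in section 3.2.

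Clinical care is unchanged. The cost is protocol wording and a few more retained records. If scores are collected after incomplete CA, those patients keep assessments that the present rule would end, with none added beyond what a completer has. The CA result may look less favourable.
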